4.4.2 Secondary Endpoints

- 4.4.2.1 To determine if 50 mg/day Modafinil improves motor function in PD patients with FOG compared to placebo as measured by the UPDRS Part III motor subscale after 12 weeks of active treatment or placebo. Subjects who drop out of the study after at least 6 weeks of either treatment arm will be included in this analysis.
- 4.4.2.2 To describe the adverse events associated with Modafinil dosed at 50 mg/day in patients treated for 3 months (delayed start arm) and 6 months (early start arm) in Parkinson's disease patients.
- 4.4.2.3 To determine if quality of life is improved with Modafinil as measured by the PDQ-39 after 12 weeks of active treatment or placebo. Subjects who drop out of the study after at least 6 weeks of either treatment arm will be included in this analysis.
- **4.4.2.4** To determine if sleep disorders are improved with Modafinil as measured by the RBD scale and Epworth Sleepiness Scale after 12 weeks of active treatment or placebo. Subjects who drop out of the

PI: [name], PhD

Sponsor: UAMS

study after at least 6 weeks of either treatment arm will be included in this analysis.

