2.0 STUDY SUMMARY

Title	Modafinil as a novel therapy for the treatment of freezing of gait in Parkinson's disease			
Short Title	Modafinil for FOG			
Protocol Number	MODFOG01			
Phase	Pilot, feasibility			
Methodology	Randomized, placebo-controlled delayed start			
Study Duration	1 year			
Study Center(s)	Single-center			
Objectives	Safety and efficacy of Modafinil for the treatment of freezing of gait in Parkinson's disease			
Number of Subjects	Enrolling 25 for a total of 20			
Diagnosis and Main Inclusion Criteria	Idiopathic Parkinson disease with freezing of gait on stable Parkinson disease treatment for 3 months.			
Study Product(s), Dose, Route, Regimen	Modafinil 50 mg capsule oral daily, Placebo capsule oral daily			
Duration of administration	24 weeks (early-start), 12 weeks (delayed-start)			
Reference therapy	none			
Statistical Methodology	The study is a prospective repeated measures longitudinal design. A primary statistical goal is to estimate the mean response at all six time points for each group and subsequently estimate changes in the outcome measures for each study group from baseline.			

PI: [name], PhD

Sponsor: UAMS

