4.0 STUDY OBJECTIVES

This is a single-center, prospective, randomized, double-blinded, placebo-controlled, delayed-start pilot trial involving up to 25 subjects with PD and FOG. Subjects will be randomized 1:1 to early start (24 weeks active treatment) or delayed start (12 weeks placebo followed by 12 weeks active treatment) oral Modafinil 50 mg/day. Following 24 weeks of treatment, a 2 week washout of the drug will be performed with a follow-up assessment at 26 weeks.

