4.2 Secondary Objectives

- **4.2.1** To determine if 50 mg/day Modafinil improves motor function in PD patients with FOG compared to placebo as measured by the UPDRS Part III motor subscale.
- **4.2.2** To describe the adverse events associated with Modafinil dosed at 50 mg/day for 3-6 months in PD patients.
- **4.2.3** To determine if quality of life is improved with Modafinil as measured by the PDQ-39.
- **4.2.4** To determine if sleep disorders are improved with Modafinil as measured by the RBD scale and Epworth Sleepiness Scale.

PI: [name], PhD

Sponsor: UAMS

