6.0 INVESTIGATIONAL PRODUCT

6.1 Test Article

Modafinil

For this study Modafinil 50 mg oral capsules will be produced and dispensed by the UAMS pharmacy in gelatin capsules with microcrystalline cellulose as filler. Subjects will take Modafinil 50 mg capsule oral daily for either 12 weeks or 24 weeks depending upon whether they are in the early-start or delayed-start arm of the trial as described below (see Figure 1).

Placebo

For this study placebo capsules will be made of gelatin capsules filled with microcrystalline cellulose and will be identical to the Modafinil capsule. Subjects in the delayed start arm will receive 12 weeks of placebo followed by 12 weeks of Modafinil 50 mg oral daily (see Figure 1)

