9.1.2 Special Warnings and Precautions for Use

Modafinil is a controlled substance as it can be abused and/or lead to dependence. Keep in a safe place to avoid misuse and abuse.

9.1.3 In-vitro data suggests that Modafinil is a weak inducer of CYP3A activity in a concentration dependent manner and therefore may reduce the effectiveness of drugs that are substrates for CYP3A enzymes (e.g. steroidal contraceptives, cyclosporine, midazolam, triazolam). Data also suggest that Modafinil is a weak inducer of CYP1A2, CYP2B6, and CYP2C9 (warfarin and phenytoin). Modafinil is also a reversible inhibitor of CYP2C19 and therefore may increase concentrations of drugs metabolized by this enzyme (e.g. phenytoin, diazepam, propranolol, omeprazole and clomipramine). Modafinil may interact with some CNS active drugs that PD patients may be using including certain tricyclic antidepressants (TCAs) (metabolized by CYP2C19) and selective serotonin uptake inhibitors (SSRIs) (metabolized by CYP2D6). Also concomitant administration of quetiapine reduced the systemic exposure of quetiapine. A recent report of a large overdose did not result in serious harmful effects.²¹

9.1.4 Adverse Events:

The following serious adverse reactions have been reported in the FDA approved label for Modafinil and will be monitored for including:

- serious rash (0.8%) including Stevens-Johnson Syndrome
- Angioedema and Anaphylaxis (one case reported out of 1595 patients)
- multi-organ hypersensitivity reactions
- persistent sleepiness
- psychiatric symptoms (0.3% including: mania, delusions, suicidal ideations, paranoid delusions, auditory hallucinations with doses of 600 mg/day)
- effect on ability to drive and use Machinery
- cardiovascular events (chest pain, palpitations, dyspnea, ischemic T-wave changes on electrocardiogram [occurred in 3 subjects with mitral valve prolapse or left ventricular hypertrophy], one episode of 9-seconds of asystole in a 35 year-old obese narcoleptic male with a prior history of syncope on 300 mg/day modafinil)

The following adverse reactions were reported in placebo controlled trials of Modafinil in Narcolepy, obstructive sleep apnea and shift work disorder in 1% or more of the modafinil treated group.

	modafinil (%) (n=934)	placebo (%) (n=567)
Headache	34	23
Nausea	11	3
Nervousness	7	3
Rhinitis	7	6
Back Pain	6	5
Diarrhea	6	5
Anxiety	5	1

Study Title: Modafinil for FOG (UAMS IRB#206341) PI: [name], PhD

Sponsor: UAMS

Dizziness	5	4
	5	4
Dyspepsia Insomnia	5	1

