10.0 STATISTICAL CONSIDERATIONS

The study is a prospective repeated measures longitudinal design. The primary outcome response is the FOG-Q total score and the stride length changes, and the secondary responses are the UPDRS Part III subscale, the PDQ-39, the RBD scale, and the Epworth Sleepiness Scale. These measures will be observed at 6 time points for both study arms. A primary statistical goal is to estimate the mean response at all six time points for each group and subsequently estimate changes in the outcome measures for each study group from baseline. Additionally, it is of interest to estimate the how the study groups differ in their mean change from baseline. A two group repeated measures linear model will be employed to determine significance for within each group and then to compare among the groups. Significance will be declared at the 5% level of significance and Bonferroni methods will be used for multiple comparisons. This analysis approach will be applied to the primary and secondary responses.

The study calls for 10 subjects in both arms for a total of 20 patients. Within a study arm the linear model will have in excess of 80% power to detect a 1.75 unit difference in observed means. Based on standard deviation estimates from previous researchers in similar settings,²² the FOGQ (the primary response) has a standard deviation of 3.58. This implies that we will have power to detect a 6.265 (1.75*3.58) unit difference among time point means at the 5% level of significance. Power calculations are from 'Tables of Sample Sizes in the Analysis of Variance' published by Bratcher.²³

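### The adverse-event endpoint groups events by arm as 3 and 6 months of modafinil and plans no use of the randomised placebo phase as a safety control

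*Combined protocol and SAP*

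**What the plan says.** The Study Summary (section 2.0) names safety alongside efficacy as the objective. Objective 4.2.2 is "To describe the adverse events associated with Modafinil dosed at 50 mg/day for 3-6 months in PD patients". Endpoint 4.4.2.2 turns this into a description by arm: "in patients treated for 3 months (delayed start arm) and 6 months (early start arm").

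The endpoints around it are framed differently. Endpoint 4.4.2.1, for example, is "compared to placebo as measured by the UPDRS Part III motor subscale after 12 weeks of active treatment or placebo". Endpoints 4.4.2.3 and 4.4.2.4 use the same 12-week, active-or-placebo frame. Only the adverse-event endpoint leaves placebo out.

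The design does contain a placebo control. Section 6.1 states: "Subjects in the delayed start arm will receive 12 weeks of placebo followed by 12 weeks of Modafinil". Section 4.0 describes the trial as randomised 1:1 and double-blinded.

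Section 10.0 lists four secondary responses (UPDRS Part III, PDQ-39, RBD scale, Epworth) and does not mention adverse events. Section 9 covers definitions, severity, attribution and reporting, but gives no tabulation plan.

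**The concern.** A description of events under modafinil needs something to set them against. This trial has a randomised, blinded, concurrent placebo group for 12 weeks, and the plan does not say it will be used for safety.

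Three things follow from the wording as it stands:

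- The two groups described differ two-fold in time on modafinil. A higher count in the early-start arm is expected even if the event rate is the same in both arms and does not change with duration.
- No concurrent background rate accompanies the description, in a population with many symptoms of its own.
- Adverse events are defined for anyone receiving study treatment (9.3.1), and every treated patient is evaluable for toxicity (6.3), so placebo-phase events will be recorded. The endpoint does not say whether delayed-start events in weeks 0-12 are left out, counted under that arm, or shown as placebo events. The choice changes the picture.

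At stake is how the safety results of a pilot are read when a later trial is considered.

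**Working it through.** **Inputs**

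- Modafinil duration (section 2.0): "24 weeks (early-start), 12 weeks (delayed-start").
- Sequence in the delayed arm (section 4.0): "delayed start (12 weeks placebo followed by 12 weeks active treatment").
- Sample size (section 10.0): "The study calls for 10 subjects in both arms for a total of 20 patients".
- Illustrative event rates from the table in 9.1.4, introduced with "The following adverse reactions were reported in placebo controlled trials of Modafinil": headache 34% on modafinil and 23% on placebo.

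**The plan's own figure.** The 6 and 3 months in 4.4.2.2 agree with the 24 and 12 weeks of modafinil in section 2.0. Ratio: 24/12 = 2.0.

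**Exposure, if all 20 complete**

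- Early start, modafinil: 10 × 24 = 240 patient-weeks.
- Delayed start, modafinil: 10 × 12 = 120 patient-weeks.
- Delayed start, placebo: 10 × 12 = 120 patient-weeks, which is 120/480 = 25% of all treatment time.
- Grouping as planned: 240 versus 120, ratio 2.0.
- Weeks 0-12 as randomised: 10 × 12 = 120 on modafinil versus 10 × 12 = 120 on placebo, ratio 1.0.

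**What duration alone does.** At equal, constant rates, event counts differ by a factor of 2.0. For patients with at least one event, let q be the 12-week risk. The 24-week risk is 1 − (1 − q)², so the ratio is [1 − (1 − q)²]/q = 2 − q. The documents give no q for this population. Over an assumed range:

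| q (12 weeks) | 24-week risk | ratio |
|---|---|---|
| 10% | 19% | 1.9 |
| 20% | 36% | 1.8 |
| 30% | 51% | 1.7 |
| 40% | 64% | 1.6 |

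None of these ratios involves any drug effect.

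**What the unstated handling does.** Assume, for illustration only, that the headache percentages apply per 12 weeks, with constant hazard and independent periods.

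- Early start, 24 weeks on modafinil: 1 − 0.66² = 56%.
- Delayed start, modafinil weeks only: 34%. Ratio 0.564/0.34 = 1.66.
- Delayed start, placebo weeks counted under the arm: 1 − 0.66 × 0.77 = 49%. Ratio 0.564/0.492 = 1.15.

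The same underlying rates give a ratio of 1.66 or 1.15 depending on a rule the plan does not state.

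**What the weeks 0-12 comparison can deliver.** With 34% versus 23%, 10 per arm and a two-sided 5% level, power is about 8% by the normal approximation and about 2% by Fisher's exact test. It can describe; it cannot test.

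**The case against.** The strongest reply is that 4.4.2.2 sets out only to describe events in a 20-patient pilot. It plans no test of 6 against 3 months and claims nothing about cumulative harm. It states the two durations openly. The data will support more than the endpoint sentence says: collection is double-blind, baseline adverse events are assessed (7.1.7), and each event receives an attribution that includes an unrelated category (9.4). Nothing forbids a placebo-phase table, and sections 6.2 and 6.7 already provide a washout visit to look for withdrawal effects.

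Much of this stands, and it rules out several stronger readings that a reader might infer:

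- *That the arm labels misstate exposure.* They do not. The 3 and 6 months are the modafinil durations in section 2.0.
- *That most listed events are common on placebo.* The 9.1.4 table does not show this: 22 rows are at 0% on placebo, including tremor and dyskinesia. The placebo rate is 23/34 = 68% of the modafinil rate for headache but 3/11 = 27% for nausea and 1/5 = 20% for anxiety. The table comes from narcolepsy, sleep apnea and shift-work trials with no follow-up time stated, so it cannot size background rates in this population.
- *That events cannot be separated from background at all.* That is true of the description as worded, not of the data.

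What the reply does not answer is that the plan states one grouping, that grouping leaves out the only randomised safety contrast, and no section supplies it. Attribution under 9.4 is a judgement made on the way to expedited reporting and is no substitute for a concurrent control.

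**Conclusion.** The point holds as a gap in the planned analysis. Adverse events are to be described by arm over 240 and 120 modafinil patient-weeks. The randomised, blinded 120 versus 120 patient-week period is not used, and the handling of delayed-start placebo events is not stated. A difference between the arms in crude counts could reflect time at risk, cumulative harm or both, and the planned description cannot tell them apart. It would go too far to say that any such difference must be due to time at risk alone.

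The patient-week figures assume 10 completers per arm with full dosing; dropout and replacement (up to 25 enrolled) would change them. The ratios of 1.6 to 1.9 and the headache illustration rest on constant hazard and on assumed 12-week risks.

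Priority is minor to moderate: the endpoint is descriptive, the trial is small, and the omission can be repaired without new visits or patients.

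**What to change.** Reword 4.2.2 and 4.4.2.2, and add a sentence to section 10.0, so that adverse events are tabulated descriptively by treatment received and by period:

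1. Weeks 0-12, modafinil versus placebo as randomised, as the main safety description.
2. All modafinil time in both arms, as events per patient-week.
3. The 2-week washout shown separately, in line with 6.2 and 6.7.

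State that delayed-start events with onset before the week-12 switch count as placebo events. Record an onset date, or at least the visit interval, for each event. The schedule in 7.3 has no adverse-event row, and no section asks for onset dates, so this must be added. Because the switch falls at Visit 3 and the washout begins at Visit 5, a visit interval is enough to place an event in its period. The pill diary (6.1.2) and the removal date (6.8) help to supply time on treatment.

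The cost is one extra table and onset recording. With 10 per arm, item 1 should be presented without significance tests and labelled as descriptive.

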4.4.3 Exploratory Endpoints

4.4.3.1 To determine if Modafinil 50 mg/day improves cognitive function in PD patients with FOG compared to placebo as measured by the Montreal Cognitive assessment, Stroop test, Frontal Assessment Battery and Scales for Outcome in Parkinson disease, Cognitive assessment (SCOPA-cog) after 12 weeks of active treatment or placebo. Subjects who drop out of the study after at least 6 weeks of either treatment arm will be included in this analysis. Additionally we will determine if at the end of 24 weeks, whether the early-start group had additional benefit of the additional 12 weeks of Modafinil treatment.

5.0 STUDY POPULATION

Eligibility waivers are not permitted. Subjects must meet all of the inclusion and exclusion criteria to be enrolled in the study. Study treatment may not begin until a subject is enrolled.

5.1 Inclusion Criteria

- Age ≥ 50 years.
- Diagnosis of idiopathic PD on UK brain bank criteria.
- Presence of FOG based on objective assessment by the movement disorders neurologist.
- FOG-Q score > 8.
- Stable PD therapy (including medications and stimulation) for a period of 3 months prior to trial enrollment.
- Women of child-bearing potential and men must agree to use adequate contraception (hormonal or barrier method of birth control; abstinence) prior to study entry, for the duration of study participation, and for 90 days following completion of therapy. Should a woman become pregnant or suspect she is pregnant while participating in this study, she should inform her treating physician immediately.
 - A female of child-bearing potential is any woman (regardless of sexual orientation, having undergone a tubal ligation, or remaining celibate by choice) who meets the following criteria:
 - Has not undergone a hysterectomy or bilateral oophorectomy; or
 - Has not been naturally postmenopausal for at least 12 consecutive months (i.e., has had menses at any time in the preceding 12 consecutive months).
- Ability to understand and the willingness to sign a written informed consent.

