Modafinil is a 1:1 racemic compound whose enantiomers have different pharmacokinetics (The half-life of R-modafinil is approximately three times that of S-Modafinil in humans). The effective elimination half-life of Modafinil is about 15 hours with linear kinetics upon multiple dosing of 200-600 mg/day with steady state reached after 2-4 days of dosing for narcolepsy. Modafinil is absorbed orally with peak plasma concentrations in 2-4 hours. The major route of elimination is metabolism (approximately 90%) by the liver with subsequent renal elimination of metabolites. In-vitro data suggests that Modafinil is a weak inducer of CYP3A activity in a concentration dependent manner and therefore may reduce the effectiveness of drugs that are substrates for CYP3A enzymes (e.g. steroidal contraceptives, cyclosporine, midazolam, triazolam). Data also suggest that Modafinil is a weak inducer of CYP1A2, CYP2B6, and CYP2C9 (warfarin and phenytoin). Modafinil is also a reversible inhibitor of CYP2C19 and therefore may increase concentrations of drugs metabolized by this enzyme (e.g. phenytoin, diazepam, propranolol, omeprazole, and clomipramine). Modafinil may interact with some CNS active drugs that PD patients may be using including certain tricyclic antidepressants (TCAs) (metabolized by CYP2C19) and selective serotonin uptake inhibitors (SSRIs) (metabolized by CYP2D6). Also concomitant administration of quetiapine reduced the systemic exposure of quetiapine.

Based on data from the [name] lab and a prior unpublished trial at the Little Rock VA on Modafinil in PTSD patients, subjects were found to be more jittery at doses of 100mg and higher (unpublished, personal communication). Therefore for this study low dose Modafinil at 50 mg orally daily will be trialed (the FDA approved recommended dosing for Narcolepsy is 200 mg/day for Narcolepsy). Additionally small studies in elderly populations suggest decreased clearance of Modafinil in elderly populations. One study showed approximately 20% decrease in oral clearance in 12 subjects given a single dose of 200 mg modafinil (mean age 63 years, range 53-72 years), while a study with multiple doses of 300 mg/day Modafinil in 12 subjects (mean age 82 years, range 67-87 years) showed mean plasma levels were two times those in historical younger subjects.

PI: [name], PhD

Sponsor: UAMS

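### Section 5.1 accepts a hormonal method alone as adequate contraception, although sections 3.2 and 9.1.3 say modafinil may weaken steroidal contraceptives; a minor inconsistency that one sentence would fix

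*Combined protocol and SAP*

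**What the plan says.** Section 5.1 (Inclusion Criteria) requires adequate contraception of men and of women of child-bearing potential. The accepted methods are given in brackets: "hormonal or barrier method of birth control; abstinence". The period covered is "prior to study entry, for the duration of study participation, and for 90 days following completion of therapy".

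A woman counts as of child-bearing potential if she meets either of two conditions: "Has not undergone a hysterectomy or bilateral oophorectomy; or" "Has not been naturally postmenopausal for at least 12 consecutive months". Tubal ligation and chosen celibacy do not take her out of the definition. A participant who is or may be pregnant is told that "she should inform her treating physician immediately".

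Section 5.0 makes the criteria binding: "Eligibility waivers are not permitted".

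On the drug, section 3.2 states: "In-vitro data suggests that Modafinil is a weak inducer of CYP3A activity in a concentration dependent manner". It draws the consequence that modafinil "may reduce the effectiveness of drugs that are substrates for CYP3A enzymes (e.g. steroidal contraceptives", with other substrates listed after. Section 9.1.3, the paragraph after the special warnings in 9.1.2, repeats both statements.

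**The concern.** The list of methods in 5.1 is joined by *or*, so a hormonal method is enough by itself. The background and the safety section both name steroidal contraceptives as drugs that modafinil may make less effective. A woman could therefore comply fully with 5.1, enter the trial, and rely throughout on the one listed type of method that the protocol flags.

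What is at stake is participant safety: an unintended pregnancy while exposed to the study drug. The contraception rule exists to prevent that, and its 90-day tail shows that the sponsor meant it cautiously. The tail lengthens the period of cover but does not change which methods count.

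**Working it through.** The plan gives no figure to reproduce, and the point does not depend on alpha, power, standard deviation or sample size. The check sets the sections side by side.

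1. **What 5.1 accepts.** One method is sufficient, and a hormonal method is on the list. No condition is attached to it.
2. **What 3.2 and 9.1.3 say about that method.** Modafinil may reduce its effectiveness. The evidence is qualified: in vitro, weak, concentration dependent. Neither section makes an exception for 50 mg.
3. **Whether another section reconciles the two.**
   - 5.2 excludes pregnant and breastfeeding individuals but says nothing about methods.
   - 6.4 restricts only antidopaminergic agents.
   - 7.1.2 and 7.1.5 provide for chart review and medication review at screening, and 7.3 schedules a medication profile at all six visits. None of these tells staff what to do on finding a hormonal contraceptive.
   - 7.4 lists pregnancy as a reason for discontinuation and puts it on the reporting timelines of a serious adverse event.
   - None of these requires a back-up method.
4. **Whether the dose was chosen to avoid the interaction.** Section 3.2 explains 50 mg by jitteriness at 100 mg and above, and adds that clearance is lower in older people. It does not mention the interaction as a reason. Section 6.3 notes that the narcolepsy dose is four times as high (200 / 50 = 4), but induction is not quantified at any dose.
5. **Who could be affected.** The upper bound is the 25 subjects allowed by 5.3; the lower bound is 0. The document gives no count of women, of premenopausal women or of hormonal users. Because the two conditions in 5.1 are joined by *or*, a literal reading also covers a postmenopausal woman who has had neither operation. The group actually at risk of pregnancy (no such surgery and not postmenopausal) is smaller. That narrower group is an assumption of this review, not the protocol's definition.
6. **For how long.** Time on modafinil, from section 6.2:
   - early start: 24 × 7 = 168 days;
   - delayed start: 12 × 7 = 84 days, in weeks 13 to 24.

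The rule in 5.1 and the warning in 3.2 and 9.1.3 thus stand together with nothing to reconcile them.

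**The case against.** The strongest reply is that this has almost no practical consequence. Entry starts at 50, freezing of gait is described in section 3.1 as a later-stage feature, and enrolment stops at 25. The warning reads like general interaction text, hedged at each step, and the dose is a quarter of the usual one. All of this stands, and it is why the point is minor. It does not remove the point. Age 50 does not exclude women who still menstruate, and the sponsor wrote a contraception rule for them. If the interaction is thought negligible at 50 mg, the protocol does not say so.

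A second reply is that safeguards exist. A hormonal contraceptive could be noticed at screening by staff whose protocol states the interaction twice, and the term *adequate* leaves some room for judgment. Pregnancy is excluded at entry, must be notified, is grounds for discontinuation and is reported promptly. These measures limit the consequences, but none makes a hormonal method alone insufficient.

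A third reply is that advice may be given elsewhere. The consent pages were not available for this review, and section 9.1 refers to the drug insert for safety updates. Such advice could close the practical gap. It would not change which methods 5.1 accepts.

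A reader might infer that contraceptive failure is to be expected at this dose, or that no safeguard exists. The documents support neither: they say only that effectiveness may be reduced, they give no size, and they contain the safeguards just listed. A reader might also extend the point to men whose partners use hormonal contraception. The interaction described concerns the person taking modafinil, so it does not reach them.

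**Conclusion.** The inconsistency is real and lies in the protocol's own text: 5.1 accepts a hormonal method alone, while 3.2 and 9.1.3 say that modafinil may weaken it. It is a conflict between a stated rule and a stated warning, not merely missing detail.

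Its size is minor. The number of women at actual risk lies between 0 and a small part of 25, and 0 is plausible. The effect of 50 mg/day on contraceptive steroids is unknown and may be small. No endpoint, estimate or power figure is affected.

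Confidence is high that the wording conflicts. That confidence does not extend to any claim of harm, which the documents do not allow one to estimate. The conclusion assumes that no unseen part of the protocol adds a back-up requirement.

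**What to change.** Keep the wording of 5.1 and add one sentence:

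> A woman of child-bearing potential who uses a hormonal method must also use a barrier method from the first dose of study drug (in either arm, because treatment is blinded) until 90 days after therapy ends, because modafinil may make steroidal contraceptives less effective; a hormonal method alone is not sufficient.

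Leave the requirement for men as it is.

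Adding a barrier method is better than asking for any non-hormonal method, since that phrase has no adequacy standard and could admit methods that 5.1 does not list. Starting at the first dose avoids ruling out hormonal-only use before there is any exposure. Applying the rule to both arms means that some women will use the back-up during 12 weeks of placebo; a rule that depended on arm would break the blind.

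The cost is a short amendment approved by the IRB before use (section 11.4), and possibly a consent update. A woman who uses a hormonal method and completes treatment would need the back-up for 168 + 90 = 258 days. Because of the *or* in the definition, the rule could also reach a few hormonal users who are not at risk of pregnancy. Any effect on eligibility should be very small, and visits, analysis and sample size do not change.
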